6.4.4 Visit #4: Day 35 ± 3 days

Visit #4 will take place 35 days ± 3 days after the Randomisation visit (visit #2) and will consist of the following procedures and examinations (to be done according to the following order and in **each eye** for ocular assessments).

By **the first investigator** in charge of all examinations and safety assessment during the investigation:

- Questioning about concomitant ocular and non-ocular treatment;
- Questioning about AEs between Day 1 or Day 8 (optional visit) and Day 35;
- Completion of DEQ-5 questionnaire;
- Measurement of OSDI score;
- Questioning about ocular symptoms;
- Measurement of the far best-corrected visual acuity;
- Measurement of conjunctival hyperaemia with McMonnies photographic scale;
- Urinary pregnancy test (only for childbearing potential women)
- Slit lamp examination with fluorescein and lissamine green stainings for measuring:
 - TBUT,
 - Oxford 0-15 grading scheme (corneal staining by fluorescein, temporal and nasal staining by lissamine),
 - Van Bijsterveld score (lissamine green staining) / optional examination;
- Schirmer test (without anaesthesia);
- Tolerance assessments by the patient and investigator;
- Performance assessment by the investigator;

At investigation sites equipped with Optical Quality Analysing System (OQAS):

- Evaluation of OSI using double pass aberrometry.

By the **second investigator** responsible for dispensation:

- Questioning about AEs between Day 1 or Day 8 (optional visit) and Day 35;
- Questioning about dose regimen compliance;
- Questioning about ocular symptoms upon instillation;
- IMD dispensation for the period Day 35 to Day 84 according to allocated treatment unit number.

6.4.5 End of investigation visit (visit #5): Day 84 ± 7 days

Visit #5 will take place 84 days ± 7 days after randomisation visit (visit #2) and will consist of the following procedures and examinations (to be done according to the following order and in both eyes for ocular assessments).

By **the first investigator** in charge of all examinations and safety assessment during the investigation:

- Questioning about concomitant ocular and non-ocular treatment;
- Questioning about AEs between Day 35 and Day 84;
- Questioning about ocular symptoms;
- Completion of DEQ-5 questionnaire;
- Measurement of OSDI score;
- Measurement of the far best-corrected visual acuity (Snellen chart);
- Measurement of conjunctival hyperaemia with McMonnies photographic scale;
- Urinary pregnancy test (only for childbearing potential women)
- Slit lamp examination for measuring:
 - TBUT,
 - Oxford 0-15 grading scheme (corneal staining by fluorescein, temporal and nasal staining by lissamine green),
 - Van Bijsterveld score (lissamine green staining) / optional examination;
- Schirmer test (without anaesthesia);
- Tolerance assessment by patient and investigator;
- Performance assessment by investigator;
- Adverse events.

At investigation sites equipped with Optical Quality Analysing System (OQAS):

- Evaluation of OSI using double pass aberrometry.

For patients with severe Dry Eye, defined as OSDI \geq 33 and/or Corneal Fluorescein Staining \geq 3 at baseline visit (Day 1):

- Impression cytology (for HLA-DR).

By the **second investigator** responsible for dispensation:

- Questioning about AEs between Day 35 and Day 84;
- Questioning about dose regimen compliance;
- Questioning about ocular symptoms upon instillation.

6.5 Procedures for the replacement of patients

The number of randomised patients will be followed in order to obtain 76 evaluable patients in the PP population.

6.6 IMD

6.6.1 Description of the exposure to the IMD

IMD will be administered by the patient every day for 84 ± 7 days, one drop in each eye 2 to 4 times daily into the lower conjunctival sac of each eye.

There will be two treatment groups:

- T2259;
- Reference product: Vismed® Multi (Appendix II)

A detailed description of T2259 is available in Section 2, page 21. Vismed® Multi is described below.

6.6.2 Justification of the choice of comparator(s)

Vismed® Multi (Horus Pharma, France) is a sterile, preservative-free, hypotonic (about 200 mOsmol/L) solution of 0.18% SH, packaged in a multidose container. Vismed® Multi is currently marketed in Europe under the CE mark as a viscoelastic lubricant eye drop (CE marking: IIb Class, notification by TÜV PRODUCT SERVIC GMB (0123), Germany). Vismed® Multi has obtained its inscription on the List of Products Reimbursed by French Social Security (LPPR) in July 2007 with the indication “Symptomatic treatment of eye dryness with keratitis or keratoconjunctivitis sicca, in third intent after failure of low viscosity tears substitutes and gels”.

[Table 4](#) details the composition and function of the comparative device Vismed® Multi. Vismed® Multi is purchased from Horus Pharma.

Packaging and labelling is provided in Section [2.6](#) page [23](#).

Table 4 Vismed® Multi

Name of ingredients	Formula Per 100 mL
HA, sodium salt	0.18%
Sodium chloride	0.279%
Potassium chloride	0.103 g
Magnesium chloride	0.0092%
Calcium chloride	0.0089%
Disodique hydrogenophosphate,	0.032%
Sodium citrate	0.0026%
Hydrochloric acid	Ad pH 7.2 – 7.4
Purified water, to	100 mL

6.6.3 List of any other medical device or medication to be used during the clinical investigation

During the run-in period, patients will be asked to use only Hydrabak® eye drops (Laboratoires Théa, France).

Hydrabak® are unpreserved NaCl 0.9 % eye drops in an ABAK® system vial containing 10 mL of solution. Hydrabak® will be provided by Laboratoires Théa.

During the selection visit (Day1 -10/Day 1 -7), the investigator in charge of all examinations and assessments will provide all patients with one bottle of Hydrabak® for the run-in treatment period between Day 1-10/Day 1-7 and Day 1.

Table 5 Run-in Medical device Sodium Chloride (Hydrabak®)

Name of the ingredients	Formula per 100 mL	Function
Sodium chloride	0.9% g	Active ingredient
Sodium dihydrogen phosphate	0.067%	Buffer
Disodium phosphate rate	0.317%	Buffer
Water for injections	Ad 100 mL	Vehicle

6.6.4 Number of IMD to be used, together with a justification

During the investigation, each patient will receive the IMD (five bottles of T2259 or of Vismed® Multi) and one bottle of Hydrabak® to cover run-in and active treatment period.

6.7 Patients

6.7.1 Inclusion criteria for patient selection

6.7.1.1 Selection visit

The following inclusion criteria have to be met at selection visit:

- Informed consent signed and dated;
- Male or female aged ≥ 18 years old;
- Known Dry Eye Syndrome requiring artificial tears within the last 3 months prior to investigation selection.

6.7.1.2 Randomisation visit

The following inclusion criteria have to be met at randomisation visit:

- Patient having used only unpreserved artificial tears (Hydrabak[®]) as ocular medication during the run-in period (from Day 1-10/Day 1 -7 to Day 1);
- No ocular instillation at least 6 hours prior to the Randomisation visit;
- Diagnosis of moderate to severe Dry Eye Syndrome defined by OSDI Score ≥ 23 ;
- Patient having at least one Eligible Eye, defined by both following conditions:
 - Total ocular staining (corneal and conjunctival) with Oxford 0-15 grading scheme ≥ 4 and ≤ 9 (e.g. patients with superficial keratitis),
AND
 - At least one of the following objective signs:
 - Schirmer test ≥ 3 mm/5 min and ≤ 9 mm/5 min,
 - OR
 - TBUT : sum of 3 measurements ≤ 30 seconds.

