Statistical method	
The aim of the study is to demonstrate the non - inferiority of T2259 with regard to Vismed® Multi in terms of performance.
 
The primary performance criterion is the change from baseline of total ocular staining grade in the worst eye on Day 35, evaluated using Oxford 0-15 grading scheme.
 
As the statistical hypothesis is the non-inferiority of T2259 with regard to Vismed® Multi, the main analysis of the primary criterion will be performed in the Per protocol population.
 
A total of 76 patients (i.e. 38 per treatment group) assume at least 90% power to establish the non-inferiority comparison on a one-sided two sample t-test with alpha=2.5 % basis (equivalent to a 95% two-sided confidence interval), assuming that the standard deviation is 2.5 and no difference between the 2 groups with a non-inferiority limit set at 2 for the change in total ocular staining grade.
 
Estimation of the standard deviation and determination of the non-inferiority limit are based upon data of previous studies and literature.
 
Concerning the non - inferiority limit, according to clinicians, a variation of 2 points in the total Oxford grade, which corresponds to a variation of less than 1 grade in the three areas (corneal, temporal and nasal), is considered as not clinically significant.
 
For taking into account approximately 15% of patients non-evaluable in Per protocol analysis (premature withdrawals without performance evaluation, patients with major protocol deviation), a total of 90 patients should be randomised in the study.

Sample size	90 randomised patients.										
Investigation Design	Multicentre, randomised study, investigator-masked, 2 parallel groups (T2259 versus Vismed® Multi) of 38 evaluable patients each.										
Investigation Duration	Run-in-period with preservative free artificial tears (Hydrabak®): from Day 1-10 or Day 1-7 to randomisation visit (Day 1) (one drop in each eye 3 to 6 times daily). 
 ▪ Treatment period: 84 ± 7 days ▪ Total study duration: maximum of 101 days 										

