Ocular medical and surgical history	X					
Systemic medical and surgical history	X					
Previous and concomitant ocular/non ocular treatments	X					
History of Dry Eye	X					
DEQ-5	X					
OSDI score						
Ocular symptoms	X					
Ocular symptoms upon instillation ⁽²⁾						
Far best-corrected visual acuity	X					
Conjunctival hyperaemia (McMonnies photographic scale)	X					

Slit lamp examination	X		X		X		X	
TBUT	X		X		X		X	
Oxford 0-15 grading scheme (corneal staining by fluorescein, temporal and nasal staining by lissamine)	X		X		X		X	
Van Bijsterveld score green (lissamine staining)/optional examination ⁽⁷⁾	X		X		X		X	
Schirmer test (without anaesthesia)								
Verification of inclusion/exclusion criteria	X		X		X		X	
Tolerance assessment by the investigator					X		X	
Tolerance assessment by the patient					X		X	
Performance assessment by the investigator					X		X	
Urinary pregnancy test ⁽²⁾	X				X		X	
Adverse events			X	X	X	X	X	X
Dispensation of the run-in treatment	X							
Run-in treatment compliance								
Dispensation of the IMD ⁽³⁾			X			X		
IMD compliance ⁽³⁾						X		X
Evaluation of Optical Scattering Index (OSI) using double pass aberrometry ⁽⁴⁾					X		X	

Impression cytology (HLA-DR) Only for patients with severe Dry Eye ⁽⁵⁾			X						X	
---	--	--	---	--	--	--	--	--	---	--

- (1) No instillation of preservative free artificial tears (Hydrabak®) at least 6 hours before the randomisation visit.
- (2) Urinary pregnancy test to be done for childbearing potential women.
- (3) By the second investigator (or the designated site team member) responsible for dispensing, explications of dosing regimen,
- (4) The parameters will be measured only in investigator sites equipped with Optical Quality Analysing System (OQAS)
- (5) Severe Dry Eye will be defined based on the following criteria: OSDI \geq 33 and/or Corneal Fluorescein Staining \geq 3 at the baseline visit (Day 1).
- (6) This visit can be performed if the investigator and /or the patient thinks it is necessary.
- (7) This examination is not mandatory

ABBREVIATIONS

ADE	Adverse Device Effect
ADDE	Aqueous Deficient Dry Eye
AE	Adverse Event
ALCOA	Attributable, Legible, Contemporaneous, Original and Accurate
ANCOVA	Analysis of Covariance
ATC	Anatomical Therapeutic Chemical
ASADE	Anticipated Serious Adverse Device Effect
AUF	Arbitrary Units of Fluorescence
BCVA	Far Best-corrected visual acuity
CIP	Clinical Investigational Plan
CMH	Cochran-Mantel-Haenszel test
e-CRF	Electronic Case Report Form

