6 DESIGN OF THE CLINICAL INVESTIGATION

6.1 General

The chosen methodology and criteria correspond to the standard usually used in the recent clinical trials in DES (HAS Optive, 2011).

Thus, this is a multicentre, randomized, investigator-masked, two parallel groups (T2259 versus Vismed® Multi) investigation in dry eye patients with superficial keratitis. The investigation will be performed in France, in Spain, in Slovakia and in Poland.

Multicenter (and multi-investigator) design will provide the possibility of recruiting the subjects from a wider population and of using the device in a broader range of clinical settings, thus presenting an experimental situation that is more typical of future use. In this case, the involvement of a number of investigators also gives the potential for a wider range of clinical judgment concerning the value of the therapeutic intervention. In addition, it is also a practical mean of accruing sufficient subjects to satisfy the study objective within a reasonable timeframe.

Because of a different visual aspect of the tested eye-drops, a double-masked comparison is not possible. Thus an investigator-masked method will be used. The identity of the IMD provided to each patient and the data concerning the instillation schedule will not be known by the investigator in charge of the examinations and of performance and safety assessments. The two different treatment units will be identical in external appearance in order to respect the randomisation. A second investigator (a physician) will dispense medications allowing to mask the first ophthalmologist investigator (who will be in charge of all examinations and assessments), and patients will be instructed not to disclose drug information with other staff members or the first investigator.

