6.4 Methods and timing for assessing, recording, and analysing variables

Five visits are scheduled during the course of the investigation as presented below:

- Visit #1: selection visit (between day 1 -10 and day 1 -7);
- Visit #2: randomisation visit (day 1);
- *Visit #3: day 8 ± 1; Optional visit (if the investigator and/or the patient thinks it is necessary)*
- Visit #4: day 35 ± 3 days;
- Visit #5: final visit (day 84 ± 7 days).

Visits V2, V3, V4 and V5 should be performed at the same hour (± 4 hours). Investigations are to be conducted as per the schedule of investigation procedures detailed in [Table 2](#), page [12](#).

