Visit dates at Day 84 and dates of withdrawal	
If DSSTAT="Completed" at the end of the study (visitnum=77, in DS table) Then ENDDT=SVSTDT where visitnum=5
 
If DSSTAT="Withdrawal" at the end of the study (visitnum=77, in DS table) Then ENDDT=DSENDDT
	End of study date	DDMMYYYY
Visit dates	
FPFV=Min (SVSTDT) where Visitnum=1
 
FPLV= MIN (ENDDT)
 
LPFV=Max (SVSTDT) where Visitnum=1
 
LPLV=Max (ENDDT)
 
FPR=Min (SVSTDT) where Visitnum=2
 
FPR=Max (SVSTDT) where Visitnum=2
	
FPFV (First Patient First Visit)
 
FPLV (First Patient Last Visit)
 
LPFV (Last Patient First Visit)
 
LPLV (Last Patient Last Visit)
 
FPR (First Patient Randomised)
	DDMMYYYY

		LPR (Last Patient Randomised)	
Visit dates	DURINC=(LPFV-FPFV+1)	Recruitment duration (in days)	Numeric (8.1)
LPLV / FPFV	DURSTYM=(LPLV-FPFV +1) /30.44	Study duration (in months)	Numeric (8.1)
Day 1 and Day 8, 35 and 84 visit dates	BS=Date of D1 SVDELi=(SVSTDATi – BS) i=Days 8, 35 and 84 (data are in line in the table)	Time between D1 and Di (in days)	Numeric (8.1)
Day 1 visit date and onset date of dry eye	DTDRYEYE=INPUT(SUBSTR(MHSTDAT, 1, 4), 8.) DEL_DRYEYE=YEAR(BS) – DTDRYEYE	Time to Dry Eye diagnosis (in years)	Numeric (8.1)
Date of randomisation visit, date and hour of last instillation of Hydrabak	SVSTD2=dhms(SVSTD, 0, 0, SVSTTIM) SVSTDAT (when visitnum=2) When ECCAT="Run-in treatment compliance": ECENDT2=dhms(ECENDT, 0, 0, ECENTIM)	Date of Day 1 Date and time of last instillation if Hydrabak	DDMMYYYY DDMMYYYY HH:MM
Date and time of randomisation and Date and time of last instillation if Hydrabak	TIME_HYD_RD= Intck("Hour", ECENDT2, SVSTD2)	Time between last instillation of Hydrabak and randomisation visit (hours)	Numeric (8.1)
Start date of Run-In period and End date of Run-In period	When ECCAT="Run-in treatment compliance" & ECCSPID in ('1' ''): RUNIN_DUR= (ECENDT – ECSTD)+1	Treatment duration in run-in period (Hydrabak) (days)	Numeric (8.1)
Treatment dosage respected during the run-in period	When ECCAT="Run-in treatment compliance" & ECCSPID in ('1' ''): If ECCOMPYN="N" Then RICOMPL=0 If ECCOMPYN="Y" Then RICOMPL=1	Compliance for run-in treatment	0="No" 1="Yes"
Start Date of Treatment, End Date of Treatment	DURTT=(ECENDT-ECSTD)+1 This derivation rule is valid for D1-D35 and D35-D84 periods	Treatment period (in days)	Numeric (8.1)

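### Time since the last drop is controlled before ocular grading on Day 1 only, leaving it uncontrolled at the Day 35 primary endpoint, and the SAP derives the Day 1 interval by counting clock-hour boundaries

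*Protocol*

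**What the plan says.** Protocol 6.7.1.2 makes a drop-free interval an inclusion criterion at randomisation: "No ocular instillation at least 6 hours prior to the Randomisation visit". Footnote 1 to Protocol Table 2 repeats it for the Day 1 column: "No instillation of preservative free artificial tears (Hydrabak®) at least 6 hours before the randomisation visit". SAP 2.2.1 and the SAP study schedule carry the same rule, again for Day 1.

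Protocol 6.4.3 to 6.4.5 list what is done at Day 8, Day 35 and Day 84. None of them sets a condition on instillation before the visit or lists the time of the last drop. At Day 35 and Day 84 the second investigator's task on dosing is "Questioning about dose regimen compliance". The timing control that spans the visits is in Protocol 6.4: "Visits V2, V3, V4 and V5 should be performed at the same hour (± 4 hours").

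The run-in regimen in the synopsis is "one drop in each eye 3 to 6 times daily"; the study products are given as "one drop in each eye 2 to 4 times daily into the lower conjunctival sac of each eye" (Protocol 6.6.1). Patients are not masked, because the drops look different and "a double-masked comparison is not possible" (Protocol 6.1).

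SAP 3.3 derives the time from the last run-in drop to the randomisation visit as "TIME_HYD_RD= Intck", with the hour as interval and no further option. SAP 6.6 summarises the result, in Tables 4.2a to 4.2c. No counterpart is derived for later visits.

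**The concern.** The primary endpoint is the change in Oxford staining from Day 1 to Day 35; TBUT and Schirmer are also analysed as changes from Day 1. The plan thought a recent drop important enough to make its absence an entry criterion, yet the second measurement in each change score is taken at an unstated time after a drop. With 2 to 4 drops a day chosen by an unmasked patient, that time can vary between patients and could vary between arms.

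In a non-inferiority trial this is not purely a loss of precision. If a recent drop masks part of a real product difference, the estimate moves towards zero, which makes a false conclusion of non-inferiority easier. No planned model would show this: the primary ANCOVA holds product and baseline, and the other models add country, COVID-19 period or visit.

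The INTCK point concerns the one interval that is measured. A variable meant to describe the 6-hour rule should not report 6 when the true interval is shorter.

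**Working it through.** **1. The plan's own figure.** Inputs from Protocol 7.5: SD 2.5, true difference 0, margin 2, one-sided 2.5%, 38 per group.

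- SE = 2.5 × √(2/38) = 0.574; noncentrality = 2/0.574 = 3.49 on 74 degrees of freedom; power = 93.1%. The stated minimum of 90% holds (34 per group would give 90.2%).
- 76/0.85 = 89.4, rounded up to 90 randomised. This reproduces.

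**2. The visits side by side.**

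| Visit | Stated condition before grading | Last-drop time |
|---|---|---|
| Day 1 | at least 6 h without a drop | date and time used in SAP 3.3 |
| Day 8 (optional) | none | not listed |
| Day 35 | none | not listed |
| Day 84 | none | not listed |

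The ± 4 h rule aligns clock time from Visit 2 onwards. Two patients seen at the same hour can still differ in when they last used a drop.

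**3. Effect of a shift common to both arms.** Write change = a + δ·arm + β·baseline + c + error, where c is the effect of recent drops at Day 35. If c is equal in both arms it goes into the intercept and δ is untouched. In 2,000 simulated trials of 76 patients, a Day 35 shift of −1.5 points in both arms left the mean ANCOVA difference at 0.00628, identical to the run without it. Each arm's own mean change moves by the full 1.5 points.

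**4. What does not cancel.** The documents give no size for a timing effect, so these are assumed ranges (38 per group, margin 2, noncentral t).

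- *Noise.* SD = √(2.5² + s²). For s = 0.5, 1.0, 1.5 the SD is 2.55, 2.69, 2.92 and power is 92.1%, 89.2%, 83.9%.
- *Attenuation.* A true deficit of 2 is observed as 2(1 − f), so the distance inside the margin is 2f. For f = 10%, 20%, 30% the chance of a false non-inferiority claim rises from 2.5% to 5.3%, 10.2%, 17.7%.
- *Arm imbalance.* A bias of b points towards T2259, with a true deficit of 2, puts the estimate b inside the margin. For b = 0.25, 0.5, 1.0 the false-claim rate is 6.3%, 13.6%, 40.6%.

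**5. The INTCK count.** With no option stated, the SAS default counts hour boundaries crossed. For a drop at m minutes past the hour and a true interval of 5 h + k min, the count is 5 + floor((m + k)/60). It equals 6 when m ≥ 60 − k, that is, for k of the 60 possible start minutes.

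- Example: 08:59 to 14:00 is 5 h 01 min but crosses 6 boundaries.
- Share read as 6: k = 1 gives 1.7%, k = 30 gives 50%, k = 59 gives 98.3%.
- Average over k = 1 to 59: (1 + 2 + … + 59)/(59 × 60) = 1,770/3,540 = 50%.
- An interval of 6 h or more is never read below 6, so errors at the threshold are all false passes.
- Over random start minutes the mean count equals the mean true interval, and each individual error is under one hour.

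**The case against.** Several stronger readings are tempting, and the documents do not support them.

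- *The baseline/follow-up mismatch biases the primary result.* Baseline is taken before randomisation under one rule for both arms, and a common mismatch cancels (step 3). Only within-arm change is affected by it.
- *Different residence times will favour one arm.* The residence-time statement in Protocol 3.3 compares a related, lower-concentration product with Hydrabak and Hyabak. Nothing compares T2259 with Vismed Multi, whose leaflet also claims a slowly dispersed film. Longer residence in normal use could also be counted as performance rather than artefact.
- *The INTCK rule lets ineligible patients stay in the per-protocol set.* The investigator verifies eligibility at Visit 2 (Protocol 6.4.2), and major deviations are settled at blind review (SAP 6.1.1). No text feeds this variable into either. SAP 6.6 only describes it, and the underlying dates and times are available.
- *Last-drop time is not recorded.* The e-CRF and the compliance diary (Protocol 6.8.4) are not among the documents; one can say only that the procedures do not list it.
- *The ± 4 h rule adds variation.* It is a control on clock time, and a useful one.

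It can also be argued that nothing is contradictory: the Day 1 rule is an entry criterion, and no passage promises the same for follow-up. That is literally so. It does not change the fact that the two measurements behind the primary endpoint have different stated conditions, with no explanation.

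What stands after all this is uncontrolled timing at Day 35, of unknown size, and a derivation that is wrong as written.

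**Conclusion.** The point holds in a limited form. The drop-free condition is stated for Day 1 only, and time since the last drop is neither set nor listed for the later gradings. The primary between-arm comparison is not biased by this if timing effects are alike in the two arms. The remaining risk is noise, attenuation or imbalance at Day 35. The ranges in step 4 show what assumed sizes would do; they do not estimate what happened. The attenuation figures apply only if T2259 is truly worse by the full margin.

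The INTCK error is real under the SAS default and confined to intervals between 5 and 6 hours, where about half would be tabulated as 6, assuming start minutes are evenly spread. How many patients fall there is unknown. It would alter the per-protocol set only if the blind review used this variable to find breaches of the criterion. It is a minor coding matter and adds no weight to the design point.

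**What to change.** 1. In SAP 3.3, compute TIME_HYD_RD as (SVSTD2 − ECENDT2)/3600, and use exact elapsed time in any blind-review check of the 6-hour criterion. Cost: one line of code.
2. Reconcile the Protocol visit passages so that baseline and follow-up gradings share one stated pre-visit instillation condition. The interval is for the sponsor's clinicians to set; none is proposed here.
3. Record the date and time of the last drop at Visits 3 to 5 and describe the interval by arm. Do not add it as a covariate: it arises after randomisation, unmasked patients can influence it, and the product may affect it, so adjustment could itself bias the comparison. Cost: one e-CRF entry per visit and minor patient inconvenience.
4. SAP 5.1 reports 101 patients already randomised, so a new field cannot recover visits already held. For those, use diary or source times where they exist; otherwise state in the report that time since the last drop at Day 35 was not controlled, and read within-arm changes with that in mind.
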